1.5 Trial estimate

HR = 0.79 (95% CI 0.66-0.96) comparing rivaroxaban vs warfarin (Patel et al., 2011)

2. Person responsible for implementation of replication in Aetion

[name], [name]., and [name], MPH implemented the study design in the Aetion Evidence Platform. They are not responsible for the validity of the design and analytic choices. All implementation steps are recorded and the implementation history is archived in the platform.

[figure not shown]
3. Data Source(s)

United/Optum, Truven/MarketScan, Medicare

4. Study Design Diagram

The study design diagram visualizes key aspects of the longitudinal study design for expedited review.

Design Diagram – ROCKET AF TRIAL REPLICATION

^aCensoring criteria

- Occurrence of outcome
- Specified Date reached
- Death
- Switch (within comparison grp)
- Start of additional Exposure
- Nursing home admission
- End of index exposure
- Disenrollment

5. Cohort Identification

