5.2 Important steps for cohort formation

New users (defined as no use in 180 days prior to index date) of an exposure and a comparator drug will be identified.

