5.3 Flowchart of the study cohort assembly

For rivaroxaban vs. warfarin

	Optum		Truven		Medicare	
	Less Excluded Patients	Remaining Patients	Less Excluded Patients	Remaining Patients	Less Excluded Patients	Remaining Patients
All patients		75,894,642		200,203,908		6,886,908
Did not meet cohort entry criteria	-74,960,282	934,360	-199,073,812	1,130,096	-2,028,461	4,858,447
Excluded due to insufficient enrollment	-92,301	842,059	-95,091	1,035,005	-1,551,114	3,307,333

Excluded due to prior use of referent	-482,398	359,661	-622,538	412,467	-2,080,069	1,227,264
Excluded due to prior use of exposure	-205,565	154,096	-204,425	208,042	-660,796	566,468
Excluded because patient qualified in >1 exposure category	-7	154,089	-26	208,016	-81	566,387
Excluded based on Age	-624	153,465	0	208,016	-155	566,232
Excluded based on Gender	0	153,465	0	208,016	0	566,232
Excluded based on Inclusion #1 - Age >=18	-86	153,379	-264	207,752	-65	566,167
Excluded based on Inclusion #2 & 3 - Atrial fibrillation	-83,438	69,941	-129,172	78,580	-348,521	217,646
Excluded based on Inclusion #4	-13,297	56,644	-16,046	62,534	-36,136	181,510
Excluded based on Exclusion #1a - Mitral stenosis	-275	56,369	-154	62,380	-399	181,111
Excluded based on Exclusion #1b - Prosthetic heart valve	-1,238	55,131	-789	61,591	-3,016	178,095
Excluded based on Exclusion #1e - atrial myxoma or left ventricular thrombus	-158	54,973	-35	61,556	-234	177,861
Excluded based on Exclusion #1f - Active infective endocarditis	-279	54,694	-138	61,418	-401	177,460
Excluded based on Exclusion #2a - Active bleeding or bleeding history	-3,413	51,281	-2,716	58,702	-8,256	169,204
Excluded based on Exclusion #2b.1 - Major Surgery	-1,564	49,717	-1,561	57,141	-6,484	162,720
Excluded based on Exclusion #2b.2 - Bleeding diathesis	-1,235	48,482	-885	56,256	-3,832	158,888
Excluded based on Exclusion #2b.3 - Intracranial neoplasm, AV malformation, cerebral aneurysm	-259	48,223	-283	55,973	-422	158,466
Excluded based on Exclusion #2d - Thrombocytopenia	0	48,223	0	55,973	0	158,466
Excluded based on Exclusion #2e - Uncontrolled hypertension	-47	48,176	-105	55,868	-300	158,166
Excluded based on Exclusion #3a.1 - stroke plus disabling stroke effects	-257	47,919	-152	55,716	-847	157,319
Excluded based on Exclusion # 3a.2 - stroke	-103	47,816	-88	55,628	-642	156,677
Excluded based on Exclusion #3b - TIA	-17	47,799	-25	55,603	-123	156,554
Excluded based on Exclusion #3c - DVT & PE	-1,095	46,704	-853	54,750	-3,185	153,369

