Excluded based on Exclusion #3d.1 - Use of aspirin > 100 mg, #3d.2 - Use of fibrinolytic agents, #3d.3 - Use of Aspirin + thienopyridines, #3d.4 - Use of cangrelor, #3f - Use of CYP inhibitors, #3g - Use of CYP inducers	-1,020	45,684	-1,024	53,726	-4,503	148,866
Excluded based on Exclusion #3h – Anemia & #3i - Pregnancy	-1,382	44,302	-1,294	52,432	-6,940	141,926
Excluded based on Exclusion #3k - HIV infection	-13	44,289	-7	52,425	-12	141,914

Excluded based on Exclusion #3l - Severe renal impairment	-3,281	41,008	-2,012	50,413	-7,391	134,523
Excluded based on Exclusion #3m - Liver disease	-192	40,816	-170	50,243	-466	134,057
Excluded based on Exclusion #4a - CCI (180 days)- ICD9 and ICD10 v2	-40	40,776	-31	50,212	-400	133,657
Excluded based on Exclusion #4b - drug addiction or alcohol abuse	-157	40,619	-106	50,106	-231	133,426
Excluded based on Exclusion #4f - Non-compliance	-15	40,604	-21	50,085	-196	133,230
Final cohort		40,604		50,085		133,230

Due to CMS cell suppression policy, all values less than 11 are denoted with **

* Medicare database includes all patients using a novel oral anticoagulant and a subset of patients using warfarin during 2011-2017.

6. Variables

6.1 Exposure-related variables:

Study drug:

The study exposure of interest is initiation of rivaroxaban. Initiation will be defined by no use of rivaroxaban or a comparator in the prior 6 months before treatment initiation (washout period).

Comparator agents-

- Initiators of rivaroxaban will be compared to initiators of-
 - Warfarin

6.2 Covariates:

- Age
- Sex
- Combined Comorbidity Index (CCI), measured over the baseline covariate assessment period, defined as 180 days prior to and including index date

Covariates listed above represent only a small subset of covariates that will ultimately be controlled for in the design and analysis. We use the covariates above only for initial feasibility analyses to judge whether there is likely to be sufficient overlap between treatment groups to proceed with the study. Remaining covariates are defined only after the study has passed the initial feasibility analysis and the initial power assessment and are listed in Table 1 (**Appendix B**).

6.3 Outcome variables and study follow-up:

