6.3.2 Study follow-up

Both as-treated (AT) and intention-to-treat (ITT) analyses will be conducted with treatment defined as the index drug on day of cohort entry. Because adherence in the real-world databases is expected to be much worse than in the trial, the AT analysis is the primary analysis, as it targets the relative hazard of outcomes on treatment.

For the as-treated analyses, the follow-up will start the day after initiation of rivaroxaban and comparator and will continue until the earliest date of the following events:

- The first occurrence of the outcome of interest, unless otherwise specified for selected outcomes,
- The date of end of continuous registration in the database,
- End of the study period,
- Measured death event occurs,
- Nursing home admission
 - Nursing home admissions are considered a censoring event because the data sources utilized typically provide little to no data on a patient, particularly on drug utilization, after admission. We will utilize this as an exclusion reason for cohorts for the same reason.

- The date of drug discontinuation, defined as the date of the last continuous treatment episode of the index drug (rivaroxaban and comparator) plus a defined grace period (i.e., 10 days after the end of the last prescription's days' supply in main analyses).
- The date of augmentation or switching from exposure to comparator or vice versa or augmentation/switching to any other NOAC (e.g. switching from rivaroxaban or warfarin to apixaban would be a censoring event);
 - A dosage change on the index treatment does not fulfill this criterion
 - An added treatment that is not part of the exposure or comparator group does not fulfill this criterion

For the intention-to-treat (ITT) analyses, the censoring based on the augmentation/switching and treatment discontinuation will be replaced with a maximum allowed follow-up time of 365 days.

7. Initial Feasibility Analysis

Action report name:

For rivaroxaban vs. warfarin

Optum- <https://bwh-dope.aetion.com/projects/details/1310/results/58054/result/0>

Truven- <https://bwh-dope.aetion.com/projects/details/1313/results/58055/result/0>

Medicare- <https://bwh-dope.aetion.com/projects/details/1341/results/58058/result/0>

Date conducted: 09/02/2020

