Appendix A

#	ROCKET-AF trial definitions	Implementation in routine care	References/Rationale	Color coding
	Trial details- Primary indication, 4a- Unintended S with label change HR = 0.79 (95% CI 0.66-0.96)		
Please see the following Google Drive for further details or any missing information: https://drive.google.com/open?id=1WDb18wvwIIfakell7cuK-VCmb6b-gV
	Criteria
			
ICD-10 codes are not listed in this document because of excel file size limitations and excessive number of ICD-10 codes. Full ICD-10 code lists will be available in the above Google Drive Folder (link above). ICD-9 to ICD-10 code conversions were completed using a SAS macro that implements forward/ backward mapping based on the CMS ICD-9 to ICD-10 mapping: https://www.ncbi.nlm.nih.gov/pmc/articles/PMC3070730/
	Adequate mapping in claims
		EXPOSURE vs. COMPARISON		
	Rivaroxaban vs. Warfarin	Rivaroxaban 20mg OR 15mg daily (if low GFR) vs. adjusted-dose warfarin		Intermediate mapping in claims
		PRIMARY OUTCOME		Poor mapping or cannot be measured in claims

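### Prior use of another NOAC is neither washed out nor recorded: as written it is an unmeasured potential confounder of unknown, possibly small, size

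*Combined protocol and SAP*

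**What the plan says.** Section 5.2 sets the entry rule: "New users (defined as no use in 180 days prior to index date) of an exposure and a comparator drug will be identified". Section 6.1 repeats it: "Initiation will be defined by no use of rivaroxaban or a comparator in the prior 6 months before treatment initiation (washout period". Warfarin is the only comparator listed.

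The flowchart in section 5.3 has two prior-use rows, one for the referent and one labelled "Excluded due to prior use of exposure". Section 5.2.2 says that Appendix A defines all entry criteria and that the flowcharts summarise them. No Appendix A criterion names another NOAC. The nearest, exclusion 3c (another indication for anticoagulation), is implemented through PE and DVT diagnoses and uses no drug codes.

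The anticoagulant covariates in Appendix B are heparins, fondaparinux or bivalirudin, and three other thrombin inhibitors (lepirudin, desirudin, argatroban). Vitamin K therapy and counts of PT and INR tests are also listed.

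Other NOACs matter after index. In the as-treated analysis, which is primary, section 6.3.2 says that "switching from rivaroxaban or warfarin to apixaban would be a censoring event". The censoring table in section 9 accordingly has a row for switches to other NOACs, combined with nursing home admission.

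**The concern.** A patient who stopped apixaban shortly before the index date passes the written washout and is counted as an initiator. That patient has already been anticoagulated and is changing treatment, possibly for a reason related to stroke or bleeding risk. If the share of such patients differs between the matched arms, and their risk differs from that of the others, the HR carries residual confounding. The planned tables could not show it, because the history is not among the listed covariates.

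The post-index rule makes the gap more noticeable. The plan already regards another NOAC as relevant enough to end as-treated follow-up, so it evidently has a definition for those dispensings, yet it does not apply one before index.

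**Working it through.** **1. Is a prior-NOAC exclusion hidden in the flowchart?** Inputs: all 32 exclusion rows in section 5.3. Subtracting them from the starting counts gives the stated final cohorts exactly:

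- Optum: 75,894,642 to 40,604
- Truven: 200,203,908 to 50,085
- Medicare: 6,886,908 to 133,230

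The two prior-use rows also close. In Optum, for example, 842,059 − 482,398 = 359,661, and 359,661 − 205,565 = 154,096. No exclusion is therefore hidden between rows. This does not show what lies inside the first step, labelled "Did not meet cohort entry criteria", which is not itemised.

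The unmatched totals in Appendix B are slightly lower: 25,701 + 14,869 = 40,570, 32,295 + 17,748 = 50,043 and 92,403 + 40,652 = 133,055. The differences are 34, 42 and 175. Nothing links them to NOAC use.

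**2. Is there a count of prior users?** No. The only NOAC-related count is 13,477 of 102,636 (13.13%) in the section 9 censoring table. It is post-index and pooled with nursing home admission, so it says nothing about history at entry.

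**3. How far could the HR move?** All inputs here except the arm size are assumptions. Let p1 and p0 be the shares of prior-NOAC patients in the two matched arms, and k their event risk relative to the others, given the matched covariates.

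Shift = (1 + p1(k − 1)) / (1 + p0(k − 1)) − 1

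With p0 = 0 and p1 = 1% (about 513 of 51,318 patients):

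| k | Shift from a 1-point difference | Difference needed for a 5% shift |
|---|---|---|
| 1.2 | 0.2% | 25 points |
| 1.5 | 0.5% | 10 points |
| 2.0 | 1.0% | 5 points |

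The shift depends on the difference between arms. Equal shares give none, whatever their level. The direction can go either way: at k = 2.0 a 1-point difference moves 0.79 to 0.79 × 1.01 = 0.798 or to 0.79 / 1.01 = 0.782. With D = 1,034.6 expected events (section 10), SE(ln HR) = 2/√1,034.6 = 0.0622, so a 1% shift is ln 1.01 / 0.0622 = 0.16 standard errors.

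**4. What would a sensitivity analysis cost in power?** Power = Φ(√(D/4) × |ln 0.79| − 1.96).

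- Stated pooled figure, D = 1,034.6: 16.08 × 0.2357 − 1.96 = 1.83, giving 0.9665. Section 10 states 0.96645, so it is reproduced.
- 5% of events lost, D = 982.8: 0.9586
- 10% lost, D = 931.1: 0.9491
- Medicare alone, 5% lost, D = 748.7 × 0.95 = 711.3: 0.8817, against 0.8971 stated

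Pooled non-inferiority power at margin 1.46 stays above 99.9% in both pooled cases.

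**The case against.** The strongest reply is that the plan does what it says. It defines new use of two named drugs, applies that rule, and never claims that patients are anticoagulant-naive. Entry criteria were adapted from the trial, and none of the trial criteria listed in Appendix A excludes prior anticoagulant use. A washout of every oral anticoagulant would make the population narrower than those criteria require. This stands, and it is why a longer list of washout drugs should not be demanded.

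The match also balances much of what might travel with a prior NOAC: in the pooled data CHADS2 is 3.11 in both arms, HAS-BLED 3.47 in both, INR tests 0.41 against 0.39, and cardiologist prescriber 63.7% against 62.6%. This reduces the concern without removing it, because none of these variables identifies NOAC use.

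A rule may also exist out of sight. Of the diagram in section 4 the text says "The study design diagram visualizes key aspects of the longitudinal study design for expedited review", but the figure is not reproduced. Appendix A adds: "Please see the following Google Drive for further details or any missing information". The nursing home exclusion announced in section 6.3.2 has no flowchart row either, so the flowchart's silence is not conclusive. This stands as a limit.

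A reader might infer more from the footnote to the flowchart: "Medicare database includes all patients using a novel oral anticoagulant and a subset of patients using warfarin during 2011-2017". It is tempting to conclude that prior-NOAC patients must be over-represented in the Medicare warfarin arm. The documents do not say how the subset was drawn, and they give no prior-NOAC share from which to estimate such an effect. Nor is the unmatched warfarin-to-rivaroxaban ratio low there: 92,403/40,652 = 2.27, against 1.73 in Optum and 1.82 in MarketScan. Age and calendar window differ between databases, so this settles nothing, but the inference is unsupported.

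**Conclusion.** The gap holds as a statement about the written plan: the washout names only rivaroxaban and warfarin, no listed criterion or covariate captures another NOAC before index, and no count is given. It amounts to an unmeasured potential confounder.

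A reader might infer that sections 6.1 and 6.3.2 contradict each other. They do not: one defines entry and the other defines the end of as-treated exposure, and a plan may set the two differently. A reader might also infer that the HR is biased in a known direction. Nothing in the documents supports that. The size is unknown and may be small: 0.2% to 1.0% per point of difference between arms, on assumed risk ratios of 1.2 to 2.0.

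The point is still worth acting on, because the variable can probably be built from definitions already in use and the adjustment is cheap. Confidence is medium, given the material that could not be seen.

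**What to change.** First state in sections 5.2 and 6.1 whether the washout covers other NOACs. If a restriction already applies, that sentence closes the point. If not:

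- add any other-NOAC dispensing in the 180 days before index to the propensity score covariates;
- report it by arm and database in Table 1, before and after matching;
- pre-specify a sensitivity analysis that excludes these patients.

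The cost is a re-run of the match and balance table. The section 10 reviews are already dated 9/8/20 and 9/29/20, so an updated balance and power summary would have to go back through that step. Sections 13 and 14 show no comparative results, so as documented the change can still come first. The existing NOAC switch row is pooled with nursing home admission, and that definition may need separating before it is reused. The sensitivity analysis would have slightly fewer patients, with pooled superiority power of about 95.9% if 5% of events are lost.

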6.3.1 Outcome variables

Primary Effectiveness outcomes of interest (definitions provided in **Appendix A**):

- Primary outcome: stroke (hemorrhagic, ischemic) and systemic embolism
- Secondary outcome: Individual components
 - Hospital admission for stroke (principal diagnosis position)
 - Hospital admission for systemic embolism (principal diagnosis position)

Control outcomes of interest (control outcomes only serve to assess aspects of study validity but are not further interpreted):

1. Major bleeding

6.3.2 Study follow-up

Both as-treated (AT) and intention-to-treat (ITT) analyses will be conducted with treatment defined as the index drug on day of cohort entry. Because adherence in the real-world databases is expected to be much worse than in the trial, the AT analysis is the primary analysis, as it targets the relative hazard of outcomes on treatment.

For the as-treated analyses, the follow-up will start the day after initiation of rivaroxaban and comparator and will continue until the earliest date of the following events:

- The first occurrence of the outcome of interest, unless otherwise specified for selected outcomes,
- The date of end of continuous registration in the database,
- End of the study period,
- Measured death event occurs,
- Nursing home admission
 - Nursing home admissions are considered a censoring event because the data sources utilized typically provide little to no data on a patient, particularly on drug utilization, after admission. We will utilize this as an exclusion reason for cohorts for the same reason.

- The date of drug discontinuation, defined as the date of the last continuous treatment episode of the index drug (rivaroxaban and comparator) plus a defined grace period (i.e., 10 days after the end of the last prescription's days' supply in main analyses).
- The date of augmentation or switching from exposure to comparator or vice versa or augmentation/switching to any other NOAC (e.g. switching from rivaroxaban or warfarin to apixaban would be a censoring event);
 - A dosage change on the index treatment does not fulfill this criterion
 - An added treatment that is not part of the exposure or comparator group does not fulfill this criterion

For the intention-to-treat (ITT) analyses, the censoring based on the augmentation/switching and treatment discontinuation will be replaced with a maximum allowed follow-up time of 365 days.

7. Initial Feasibility Analysis

Action report name:

For rivaroxaban vs. warfarin

Optum- <https://bwh-dope.aetion.com/projects/details/1310/results/58054/result/0>

Truven- <https://bwh-dope.aetion.com/projects/details/1313/results/58055/result/0>

Medicare- <https://bwh-dope.aetion.com/projects/details/1341/results/58058/result/0>

Date conducted: 09/02/2020

Complete Aetion feasibility analysis using age, sex, and CCI as the only covariates and the primary endpoint (Section 6.3.1) as the outcome. No measures of association will be computed nor will incidence rates stratified by treatment group.

- Report patient characteristics by treatment group
- Report summary parameters of study population
- Report median follow-up time by treatment group
- Report reasons for censoring in the overall study population

8. Initial Power Assessment

Action report name:

For rivaroxaban vs. warfarin

Optum- <https://bwh-dope.aetion.com/projects/details/1310/results/58056/result/0>

Truven- <https://bwh-dope.aetion.com/projects/details/1313/results/58057/result/0>

Medicare- <https://bwh-dope.aetion.com/projects/details/1341/results/58059/result/0>

Date conducted: 09/02/2020

In order to complete the initial power analysis, the dummy outcome of a 90-day gap in database enrollment will be used. This outcome is used to ensure that no information on the comparative risks of the outcomes of interest are available at this stage. Complete a 1:1 PS-matched comparative analysis using this outcome. PS should include only 3 covariates: age, sex, and combined comorbidity index. Power calculations are based on the formulas from Chow et al. (2008).

- Stop analyses until feasibility and power are reviewed by primary investigators and FDA. Reviewers evaluate the results of the analyses described above in Sections 7 and 8, including numbers of patients, patient characteristics, follow-up time, and reasons for censoring by treatment group, as well as overall rates of outcomes and study power. These parameters are re-evaluated and reported in the subsequent sections, after incorporating feedback and refining the protocol.

Reviewed by PI:	[name]	Date reviewed:	6/3/20
Reviewed by FDA:	[name]	Date reviewed:	6/30/20
Reasons for stopping analysis (if required):			

9. Balance Assessment

Action report name:

Optum- <https://bwh-dope.aetion.com/projects/details/1310/results/57933/result/0>

Marketscan- <https://bwh-dope.aetion.com/projects/details/1313/results/57934/result/0>

Medicare- <https://bwh-dope.aetion.com/projects/details/1341/results/57981/result/0>

Date conducted: 8/27/2020 (Medicare 8/30/2020)

After review of initial feasibility and power analyses, complete creation of the remaining covariates (see Table 1 below for list of covariates). Again, using the dummy outcome of a 90-day gap in database enrollment, complete a 1:1 PS-matched analysis. The PS should include the complete list of covariates (excluding laboratory values, which are missing in some patients).

- Provide plot of PS distributions stratified by treatment group.

Note- Please refer to **Appendix B**.

- Report covariate balance after matching.

Note- For Table 1, please refer to **Appendix B**.

- Report reasons for censoring by treatment group.

	Overall	Referent	Exposure
Dummy Outcome	0 (0.00%)	0 (0.00%)	0 (0.00%)
Death	1,879 (1.83%)	946 (1.84%)	933 (1.82%)
Start of an additional exposure	3,238 (3.15%)	1,642 (3.20%)	1,596 (3.11%)
End of index exposure	71,983 (70.13%)	36,022 (70.19%)	35,961 (70.07%)
Specified date reached (Dec 17/Dec 18/Dec 19)	6,822 (6.65%)	3,196 (6.23%)	3,626 (7.07%)
End of patient enrollment	5,237 (5.10%)	2,408 (4.69%)	2,829 (5.51%)
Switch to other NOACs (for censoring) + nursing home admission	13,477 (13.13%)	7,104 (13.84%)	6,373 (12.42%)

- Report follow-up time by treatment group.

Median Follow-Up Time (Days) [IQR]			
Patient Group	Optum	Truven	Medicare
Overall Patient Population	98 [38-209]	98 [44-236]	98 [38-206]
Referent	98 [38-190]	98 [44-192]	98 [38-188]
Exposure	98 [38-231]	119 [44-281]	98 [38-228]

- Report overall risk of the primary outcome.

	Optum	MarketScan	Medicare	Pooled
Risk per 1,000 patients	7.00	7.33	12.05	10.08

10. Final Power Assessment

Date conducted:

- Re-calculate power in the appropriate excel table, using the revised number of matched patients from the PS-match in Section 9. All other parameters in the table should be the same as in Section 8.

- For rivaroxaban vs. warfarin

- Pooled

Superiority Analysis		Non-inferiority Analysis	
Number of patients matched	102,636	Number of patients matched	102,636
Reference	51,318	Reference	51,318
Exposed	51,318	Exposed	51,318
Risk per 1,000 patients	10.08	Risk per 1,000 patients	10.08
Desired HR from RCT	0.79	Assumed HR from RCT	1
Alpha (2-sided)	0.05	Alpha (2-sided)	0.05
		Non-inferiority margin	1.46
Number of events expected	1034.57088	Number of events expected	1034.57088
Power	0.966450516	Power	0.999981559

o Optum

Superiority Analysis		Non-inferiority Analysis	
Number of patients matched	17,900	Number of patients matched	17,900
Reference	8,950	Reference	8,950
Exposed	8,950	Exposed	8,950
Risk per 1,000 patients	7.00	Risk per 1,000 patients	7.00
Desired HR from RCT	0.79	Assumed HR from RCT	1
Alpha (2-sided)	0.05	Alpha (2-sided)	0.05
		Non-inferiority margin	1.46
Number of events expected	125.3	Number of events expected	125.3
Power	0.261393559	Power	0.562809862

o MarketScan

Superiority Analysis		Non-inferiority Analysis	
Number of patients matched	22,600	Number of patients matched	22,600
Reference	11,300	Reference	11,300
Exposed	11,300	Exposed	11,300
Risk per 1,000 patients	7.33	Risk per 1,000 patients	7.33
Desired HR from RCT	0.79	Assumed HR from RCT	1
Alpha (2-sided)	0.05	Alpha (2-sided)	0.05
		Non-inferiority margin	1.46
Number of events expected	165.658	Number of events expected	165.658
Power	0.329138572	Power	0.682759594

- Medicare

Superiority Analysis		Non-inferiority Analysis	
Number of patients matched	62,136	Number of patients matched	62,136
Reference	31,068	Reference	31,068
Exposed	31,068	Exposed	31,068
Risk per 1,000 patients	12.05	Risk per 1,000 patients	12.05
Desired HR from RCT	0.79	Assumed HR from RCT	1
Alpha (2-sided)	0.05	Alpha (2-sided)	0.05
		Non-inferiority margin	1.46
Number of events expected	748.7388	Number of events expected	748.7388
Power	0.897079133	Power	0.999353731

- Stop analyses until balance and final power assessment are reviewed by primary investigators, FDA, and assigned members of advisory board.

Reviewed by PI:	[name]	Date reviewed:	9/8/20
Reviewed by FDA:	[name]	Date reviewed:	9/29/20
Reasons for stopping analysis (if required):			

11. Study Confidence and Concerns

Deadline for voting on study confidence and listing concerns:

Date votes and concerns are summarized:

- If final feasibility and power analyses are reviewed and approved, proceed to the remaining protocol steps.

- All study team and advisory board members that review this protocol should at this stage provide their level of confidence for the success of the RWD study in the [Google Form](#). This form also provides space for reviewers to list any concerns that they feel may contribute to a failure to replicate the findings of the RCT, including differences in study populations, poor measurement of study variables, or residual confounding. All responses will be kept confidential and individual-level results will only be shared with the individual respondent.
- After the deadline for voting has passed, provide the distribution of responses and summarize all concerns here.

12. Register study protocol on clinicalTrials.gov

Date conducted:

- Register the study on [clinicalTrials.gov](#) and upload this document.

13. Comparative Analyses

Action report name:

Date conducted:

13.1 For primary analysis:

13.2 For sensitivity analyses:

14. Requested Results

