5.2.2 Specify inclusion/exclusion criteria for cohort entry and define the index date

Inclusion and exclusion criteria were adapted from the trial as closely as possible. Definitions for all inclusion/exclusion are provided in **Appendix A** and are summarized in the flowcharts below.

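### Does the nursing-home exclusion promised in Section 6.3.2, which Appendix A and the flowchart never name, call for a change to the plan?

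*Combined protocol and SAP*

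**What the plan says.** Section 6.3.2 lists nursing-home admission among the events that end as-treated follow-up. The reason given is that the data sources typically hold little or nothing on a patient, drug use above all, once the patient is admitted. It extends the rule to cohort entry: "We will utilize this as an exclusion reason for cohorts for the same reason". The ITT paragraph of the same section replaces only the switching and discontinuation rules, so nursing-home censoring stays in both analyses.

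Section 5.2.2 says where criteria are to be found: "Definitions for all inclusion/exclusion are provided in" Appendix A, and they "are summarized in the flowcharts below". Appendix A sets each trial criterion beside its claims implementation, and no row concerns nursing homes. The Section 5.3 flowchart has 32 removal rows, and none names it. Elsewhere in the readable text, nursing-home admission appears only as censoring: in the list under the design diagram (Section 4) and in the Section 9 censoring table, where it shares a row with switching to other NOACs.

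**The concern.** A stated exclusion with no codes, care setting, look-back or count looks like one that was announced and then forgotten. Two easy excuses fail.

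- That it is a data rule rather than a trial criterion does not explain the missing row. Seven of the 32 rows carry no Appendix A number, for example "Excluded due to insufficient enrollment".
- That it may have removed nobody does not explain it either. Rows with no removals are printed, such as "Excluded based on Exclusion #2d - Thrombocytopenia", which shows 0 in all three databases.

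If the step was skipped, the matched cohort could contain patients already in a nursing home at index, for whom the protocol itself says data capture is poor. The primary analysis is as-treated and depends on dispensing records. Censoring does not settle the matter, because it responds to admissions during follow-up and not to status at baseline.

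**Working it through.** **1. Does the flowchart account for every removal?** Within itself, yes. Subtracting the 32 rows in turn from 75,894,642 / 200,203,908 / 6,886,908 (Optum / MarketScan / Medicare) gives 40,604 / 50,085 / 133,230 with no mismatch, a total of 223,919. The patients who reached the unmatched table in Appendix B are fewer:

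| | Flowchart final | Appendix B unmatched (warfarin + rivaroxaban) | Difference |
|---|---|---|---|
| Optum | 40,604 | 25,701 + 14,869 = 40,570 | 34 |
| MarketScan | 50,085 | 32,295 + 17,748 = 50,043 | 42 |
| Medicare | 133,230 | 92,403 + 40,652 = 133,055 | 175 |
| Total | 223,919 | 223,668 | 251 |

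251 / 223,919 = 0.11%. The documents do not explain this drop, so it cannot be read as the nursing-home exclusion. It does show that at least one removal has no flowchart row, so the lack of a row is not evidence that a step was skipped.

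**2. Where else could the exclusion sit?** The first row, "Did not meet cohort entry criteria", removes 74,960,282 / 199,073,812 / 2,028,461 patients without itemising them. The design diagram is not reproduced in the text available. Appendix A defers to linked files: "Please see the following Google Drive for further details or any missing information". Section 2 states: "All implementation steps are recorded and the implementation history is archived in the platform". Any of these could hold the definition or show that it was applied. None can be inspected from the document.

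**3. Was a nursing-home measure in use?** The Section 9 censoring counts are 0 + 1,879 + 3,238 + 71,983 + 6,822 + 5,237 + 13,477 = 102,636, which is the matched cohort of Section 10. The last entry, 13,477 (13.13%), is the row that combines NOAC switching with nursing-home admission. A nursing-home definition was therefore running in the platform when the matched cohort was produced. The row counts follow-up events, so it does not show how baseline status was handled.

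**4. Which residents could enter at all?** Section 5.1 requires an observed start of the index drug and 180 days of continuous enrollment. Appendix A requires repeated atrial fibrillation diagnoses within 12 months. A resident with no claims activity cannot qualify. Under the as-treated rule, a patient whose dispensings stop being recorded leaves follow-up 10 days after the last days' supply ends, which limits misclassified exposure time.

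**5. Are the arms alike on related characteristics?** After matching, with 51,318 per arm (warfarin vs rivaroxaban, pooled, Appendix B):

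- dementia 4,607 vs 4,552 (9.0% vs 8.9%)
- falls 1,697 vs 1,716 (3.3% vs 3.3%)
- delirium 1,409 vs 1,386 (2.7% vs 2.7%)
- mean frailty score: standardized difference 0.00 in each database

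**6. Is any stated result wrong?** Expected events are 102,636 × 10.08 / 1,000 = 1,034.57. Superiority power is Φ(|ln 0.79| × √(1,034.57 / 4) − 1.96) = 0.9665, which matches Section 10. The power table is correct on its own inputs. The number of baseline residents is given nowhere, so no corrected figure can be computed.

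**The case for a change.** The best case for a change is that Section 5.2.2 makes a promise the visible text does not keep, whether or not the exclusion was applied. On this reading the cohort cannot be reproduced from the document. Balanced dementia, falls and frailty may limit confounding, but they do not restore missing dispensing or outcome records. The entry conditions also do not rule out every resident: a patient whose earlier dispensings went unrecorded would pass the 180-day washout. Acting would be cheap, since the dates in Sections 12 and 13 are blank and the implementation history is archived.

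Most of this stands as a remark on reporting. The exclusion is undefined in the text. So is the nursing-home censoring rule, which has no codes or care setting either. None of it shows a wrong analysis. The one action that does not depend on an unknown fact is to consult the archive and write down what was done. If the exclusion was applied, nothing in the analysis moves. If only censoring was intended, rewording one sentence moves nothing either. A re-match would follow only if the step was intended and omitted, and the documents do not establish that.

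**Conclusion.** The inconsistency between Section 6.3.2 on one side and Appendix A and the flowchart on the other is real, but it is a documentation gap. Section 6.3.2 states a sensible rule with a sensible reason, and a team that follows it needs only to supply a code list and a look-back, as programmers do routinely for such rules. Whether it was applied to the 102,636 matched patients is not shown, and neither is the opposite. The 251-patient difference (34 / 42 / 175) is unexplained and cannot be assigned to any cause. No figure in Sections 9 or 10 is shown to be wrong, and the size and direction of any bias cannot be derived.

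This conclusion assumes that the implementation followed Section 6.3.2 as written. If the archive showed that the exclusion had been dropped by mistake, that would be a departure from the plan to put right in the implementation. It would not be a defect in the plan.
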